### **10.2 Case Report Forms and Source Documentation**

All data obtained during this study should be entered in the eCRF promptly. All source documents from which eCRF entries are derived should be placed in the patient's medical records. Measurements for which source documents are usually available include laboratory assessments, ECG, MRI scans, and X-rays.

The original eCRF entries for each patient will be checked against source documents at the study site by the CRA.

#### ***10.2.1 Data Collection***

The Investigators (and appropriately authorised staff) will be given access to an online web-based eCRF system called DataLabs which is 21 CFR Part 11 compliant. DataLabs is specifically designed for the collection of the clinical data in electronic format. Access rights to the eCRF system will be carefully controlled and configured according to each individual's role throughout the study. In general, only the Investigator and authorised staff will be able to enter data and make corrections in the eCRFs.

The eCRF should be completed for each patient included in the study and should reflect the latest observations on the patients participating in the study. Therefore, the eCRFs are to be completed as soon as possible during or immediately after the patient's visit or assessment. The Investigator must verify that all data entries in the eCRF are accurate and correct. If some assessments cannot be done, or if certain information is unavailable, not applicable or unknown, the Investigator should indicate this in the eCRF.

Computerised data-check programs and manual checks will identify any clinical data discrepancies for resolution. Corresponding queries will be loaded into the system and the site

will be informed about new issues to be resolved on-line. All discrepancies will be solved on-line directly by the Investigator or by authorised staff. Off-line edit checks will be done to examine relationships over time and across panels to facilitate quality data.

After completion, the Investigator will be required to electronically sign off the clinical data entered into the eCRF.

### **10.3 Access to Source Data**

During the study, a CRA will make site visits to review protocol compliance, compare eCRF entries and individual patient's medical records, assess drug accountability, and ensure that the study is being conducted according to pertinent regulatory requirements. eCRF entries will be verified with source documentation. The review of medical records will be performed in a manner to ensure that patient confidentiality is maintained.

Checking of the eCRF entries for completeness and clarity, and cross-checking with source documents, will be required to monitor the progress of the study. Moreover, Regulatory Authorities of certain countries, IECs, and/or the Sponsor's Clinical Quality Assurance Group may wish to carry out such source data checks and/or on-site audits or inspections. Direct access to source data will be required for these inspections and audits; they will be carried out giving due consideration to data protection and medical confidentiality. The Investigator assures PAREXEL and the Sponsor of the necessary support at all times.

### **10.4 Data Processing**

All data will be entered by site personnel into the eCRF (as detailed in Section 10.2.1).

Previous and concomitant medications will be coded using the World Health Organization (WHO) Drug Reference List (DRL), which employs the Anatomical Therapeutic Chemical (ATC) classification system. Medical history/current medical conditions and adverse events will be coded using the MedDRA terminology.

The versions of the coding dictionaries will be provided in the Clinical Study Report.

### **10.5 Data Monitoring**

A Trial Steering Committee (TSC) will be established and will be blinded and responsible for providing overall supervision for the study in accordance with pre-agreed terms of reference, in particular to the progress of the study, adherence to the protocol and patient safety. Operationally this will include consultation regarding the study design, subsequent amendments and emerging data and research relevant to the study, including open DMEC reports and the results of other research that may have a direct bearing on the future conduct of the study. They will also ensure that any action taken protects the rights, safety and wellbeing of patients and the study is conducted to the rigorous standards of GCP. It is anticipated that the TSC will meet at approximately 6-12 monthly intervals and after each independent DMEC review as required. Any SAE will be reported to the DMEC who may recommend stopping the study for safety reasons. Interim safety analyses (i.e. no efficacy analyses) will be undertaken after the first 25 patients have completed Visit 4 and Visit 5.

The independent DMEC will be set up to monitor study safety which will be specified in a DMEC charter. The independent DMEC will be unblinded and will include three members: an independent chair having specialist osteoarthritis expertise and experience of studies in this area, an independent statistician and a second physician. Specifically they will monitor AEs and serious SAEs related to the treatments received in accordance with the recommendations of performing a clinical study of an IMP. In addition the independent DMEC will make recommendations on continuation of the study based on interim safety analyses.

## **10.6 Safety Monitoring Plan**

A change in the value of a clinical laboratory investigation can represent an AE if the change is clinically relevant or if, during treatment with the investigational product, a shift of a parameter is observed from a normal value to an abnormal value, or a further worsening of an already abnormal value. When evaluating such changes, the extent of deviation from the reference range, the duration until return to the reference range, either while continuing treatment or after the EOT with the investigational product, and the range of variation of the respective parameter within its reference range, must be taken into consideration.

If, at the end of the treatment phase, there are abnormal clinical laboratory values which were not present at Baseline, further clinical or laboratory investigations should be performed until the values return to within the reference range or until a plausible explanation (e.g., concomitant disease) is found for the abnormal clinical laboratory values.

The Investigator should decide, based on the above criteria and the clinical condition of a patient, whether a change in a clinical laboratory parameter is clinically significant and therefore represents an AE.

## **10.7 Archiving Study Records**

According to ICH guidelines, essential documents should be retained for a minimum of 2 years after the last approval of a marketing application in an ICH region and until there are no pending or contemplated marketing applications in an ICH region or at least 10 years have elapsed since the formal discontinuation of clinical development of the investigational product. However, these documents should be retained for a longer period if required by the applicable legal requirements.

No essential documents may be destroyed without prior written approval from the Sponsor.

## **10.8 Good Clinical Practice**

The procedures set out in this study protocol are designed to ensure that the Sponsor and Investigator abide by the principles of the GCP guidelines of the ICH, and of the Declaration of Helsinki (1996). The study also will be carried out in accordance with local legal requirements.

## **10.9 Informed Consent**

Before each patient is admitted to the study, informed consent will be obtained from the patient according to the regulatory and legal requirements of the participating country. This consent form must be dated and retained by the Investigator as part of the study records. The Investigator will not undertake any investigation specifically required only for the clinical study until valid consent has been obtained. The terms of the consent and when it was obtained must also be documented in the eCRF system.

If a protocol amendment is required, the ICF may need to be revised to reflect the changes to the protocol. If the consent form is revised, it must be reviewed and approved by the appropriate IEC, and signed by all patients subsequently enrolled in the study as well as those currently enrolled in the study.

## **10.10 Protocol Approval and Amendment**

Before the start of the study, the study protocol and/or other relevant documents will be approved by the IEC/Regulatory Authorities, in accordance with local legal requirements. The Sponsor must ensure that all ethical and legal requirements have been met before the first patient is enrolled in the study.

This protocol is to be followed exactly. To alter the protocol, amendments must be written, receive approval from the appropriate personnel, and receive IEC/Regulatory Authority approval prior to implementation (if appropriate). Administrative changes (not affecting the patient benefit/risk ratio) may be made without the need for a formal amendment. All amendments will be distributed to all protocol recipients, with appropriate instructions.

#### **10.11 Duration of the Study**

The study will be conducted from September 2016 to August 2017.

#### **10.12 Confidentiality**

All study findings and documents will be regarded as confidential. The Investigator and members of his/her research team must not disclose such information without prior written approval from the Sponsor.

The anonymity of participating patients must be maintained. Patients will be identified in the eCRF system and other documents submitted to PAREXEL by their patient number and date of birth, not by name. Documents that identify the patient (e.g., the signed informed consent) must be maintained in confidence by the Investigator and should never be submitted to PAREXEL or the Sponsor.

#### **10.13 Other Ethical and Regulatory Issues**

If a significant safety issue is identified, either from an individual case report or review of aggregate data, then the Sponsor will issue prompt notification to all parties – Regulatory Authorities, Investigators, and Institutional Review Boards/IECs.

A significant safety issue is one that has a significant impact on the course of the clinical study or program (including the potential for suspension of the development program or amendments to protocols) or warrants immediate update of informed consent.

#### **10.14 Liability and Insurance**

The Sponsor will take out reasonable third-party liability insurance cover in accordance with all local legal requirements. The civil liability of the Investigator, the persons instructed by him or her and the hospital, practice, or institute in which they are employed and the liability of the Sponsor with respect to financial loss due to personal injury and other damage that may arise as a result of the carrying out of this study are governed by the applicable law.

The Sponsor will arrange for patients participating in this study to be insured against financial loss due to personal injury caused by the pharmaceutical products being tested or by medical steps taken in the course of the study.

#### **10.15 Publication Policy**

By signing the study protocol, the Investigator agrees with the use of results of the study for the purposes of national and international registration, publication and information for medical and pharmaceutical professionals. If necessary, Regulatory Authorities will be notified of the Investigator's name, address, qualifications and extent of involvement.

An Investigator shall not publish any data (poster, abstract, paper, etc.) without having consulted with the sponsor in advance.

## 12 APPENDICES

**12.1 APPENDIX 1: Total Blood Volumes**

The total volume of blood that will be drawn from each patient in this study is as follows:

Assessment	Sample Volume (mL)	No of samples	Total Volume (mL)
Safety			
• Clinical chemistry	9.5	6	57
• Haematology	2	6	12
Pharmacokinetic samples	5	3	15
Blood samples for pharmacogenomics, proteomics, genomics, metabolomics and lipidomics	19	1	19
Biomarker analysis	15	4	60
Additional unforeseeable samples			37
Total			200

12.	FIGURES	59

**PAREXEL International
Statistical Analysis Plan**

Medivir
Protocol: MIV-711-202

Final 1.0
16 January 2018

13. LISTINGS..... 61
14. TABLE SHELLS..... 63
15. LISTING SHELLS 121

PAREXEL International Statistical Analysis Plan

Medivir
Protocol: MIV-711-202

Final 1.0
16 January 2018

Abbreviations and definitions

AE	Adverse event
BLQ	Below the lower limit of quantification
BMI	Body Mass Index
BML	Bone Marrow Lesions
CI	Confidence interval
CS	Clinically significant
CV	Coefficient of variation
DMC	Data monitoring committee
ECG	Electrocardiogram
FAS	Full analysis set
h	Hour
IMP	Investigational Medicinal Product
LLOQ	Lower limit of quantification
MedDRA	Medical Dictionary for Regulatory Activities
MOAKS	MRI Osteoarthritis Knee Score
NCS	Not clinically significant
NRS	Numeric Rating Scale
NK	Not known
OA	Osteoarthritis
PK	Pharmacokinetic
PPS	Per Protocol Set
q.d.	Once a day
QOL	Quality of Life
SAE	Serious adverse event
SAP	Statistical Analysis Plan
SD	Standard deviation
SOC	System Organ Class
TEAE	Treatment-emergent adverse event
TIC	Time Integrated Concentrations
WHO-DD	World Health Organisation - Drug Dictionary

PAREXEL International Statistical Analysis Plan

Medivir
Protocol: MIV-711-202

Final 1.0
16 January 2018

1. Statistical Analysis Plan

This Statistical Analysis Plan (SAP) provides a detailed and technical description of the planned statistical evaluation of the Medivir study MIV-711-202: “An Open-Label, One-Arm Phase II Extension Study to Evaluate Safety and Tolerability of MIV-711 in Patients with Knee Joint Osteoarthritis”. The SAP also outlines the statistical programming specifications for the tables, listings and figures.

Full description of the investigational plan, selection criteria, assessments, etc. are given in the Clinical Study Protocol (CSP): MIV-711-202, dated 01 July 2016.

The planned analyses will be conducted by PAREXEL.

2. Study Objectives and Hypotheses

2.1 Primary Objective Study Group A

To assess the safety and tolerability of 200 mg MIV-711 q.d. over 52 (26+26) weeks in patients with symptomatic and radiographic knee osteoarthritis.

- Study Group A will be recruited from patients treated with 200 mg MIV-711 q.d. in Study MIV-711-201 and whose symptoms did not clinically significantly deteriorate as defined by an increase in NRS of ≤ 2 compared to Baseline.

2.2 Secondary Objectives Study Group A

To assess, in patients with symptomatic and radiographic knee OA, over 52 (26+26) weeks:

- The effect of MIV-711 on MRI cartilage thickness loss
- The effect of MIV-711 on MRI bone marrow lesion volume
- The effect of MIV-711 in the semi quantitative MRI Osteoarthritis Knee Score (MOAKS) parameters
- To assess the effect of MIV-711 on MRI knee joint bone area.

Note: all MRI assessments refer to the target knee unless stated otherwise.

Target knee is identified by knee pain on a numeric rating scale and Kellgren and Lawrence classification grade. If patients have knee pain in both sides with equal regard to these two criteria, the right knee should always be prioritized. The target knee in Study MIV-711-202 must be the same as in Study MIV-711-201.

PAREXEL International Statistical Analysis Plan

Medivir
Protocol: MIV-711-202

Final 1.0
16 January 2018

2.3 Secondary Objectives Study Group B

To assess the effect of 200 mg MIV-711 q.d. on safety and tolerability over 26 weeks in patients with symptomatic and radiographic knee osteoarthritis.

- Study Group B will be recruited from patients receiving placebo in Study MIV-711-201 having experienced a clinical worsening as defined by an increase in NRS of ≥ 2 versus Baseline.
- Data from both MIV-711-201 and MIV-711-202 studies will be used for Group B assessment

2.4 Exploratory Objectives Study Group A

Data from both MIV-711-201 and MIV-711-202 study will be used for Group A assessment.

In addition, the study will investigate the following exploratory parameters.

- The effect of MIV-711 on worst target knee pain (1 week recall)
- The effect of MIV-711 on average contralateral knee pain (1 week recall)
- The effect of MIV-711 on constant and intermittent OA pain
- The effect of MIV-711 on global improvements in knee problem, knee pain and knee function
- The effect of MIV-711 on knee joint OA symptoms (function, pain, stiffness)
- The effect of MIV-711 on global disease activity
- The effect of MIV-711 on quality of life (QoL)
- The effect of MIV-711 on patient reported e-diary daily recall knee joint pain
- The effect of MIV-711 on patient reported e-diary daily recall analgesics use
- Assessment of the effect of MIV-711 on exploratory serum and urinary biomarkers of relevance for OA including but not limited to procollagen type I N-terminal propeptide (PINP), bone specific alkaline phosphatase (BSAP), N-terminal telopeptide of collagen type I (NTX-I), CTX-I, aCTX-I, CTX-II and tartrate-resistant acid phosphatases (TRAP5b).
- Baseline and steady state treatment blood and urinary samples will be stored for patients who sign a separate voluntary Informed Consent Form (ICF) for potential future pharmacogenomics and disease-related proteomics, genomics, metabolomics and lipidomics analyses.
- The effect of MIV-711 on a compound index of MRI bone area and cartilage thickness
- The pharmacokinetics of MIV-711 and the relationship to patient actors and concomitant medications

PAREXEL International Statistical Analysis Plan

Medivir
Protocol: MIV-711-202

Final 1.0
16 January 2018

2.5 Exploratory Objectives Study Group B

All of the above noted secondary and exploratory parameters described in Section 2.2 and Section 2.4 for study group A, are considered as exploratory objectives in study group B and will be evaluated over 26 weeks on 200 mg MIV-711 succeeding 26 weeks on Placebo.

3. Study Design

This study is a 6-month open-label one-arm extension study evaluating safety and tolerability as well as the efficacy of 200 mg MIV-711 q.d. in two separate patient populations denoted as study Group A and Group B.

Study Group A patients will be recruited from Study MIV-711-201 who were treated with 200 mg MIV-711 q.d. and whose symptoms did not clinically significantly deteriorate as defined by an increase in the numeric rating scale (NRS) of ≤ 2 compared to Baseline. Patients eligible for Study Group A will be offered 6 months' extended treatment, primarily evaluating longer term safety and tolerability. The total treatment duration of 52 weeks also allows a more suitable treatment length for the exploratory study of any structural effects of MIV-711 on joint cartilage thickness.

[figure not shown]
A further rationale of this study is to explore the treatment effect in a group of OA patients that have confirmed symptom progression over the last 6 months (Study Group B). Study Group B will be recruited from patients receiving placebo in Study MIV-711-201 who experienced a clinical worsening as defined by an increase in NRS of ≥ 2 versus Baseline. Patients eligible for Study Group B will be offered 200 mg MIV-711 q.d. for the next 26 weeks. In addition to offering the treatment to appropriate patients, this also enables the assessment of the effects of MIV-711 based on MRI imaging, symptoms and biomarkers in patients with progressing symptoms and, as such, has the potential to provide valuable information for future patient selection in OA trials. Similar to Study MIV-711-201, the joint structural endpoint of choice over 6 months treatment constitutes MRI joint bone surface measurement. All analyses, with the exception of safety and tolerability, will be conducted as exploratory with regards to Study Group B.

The analysis of data from this study will not be based on a formal statistical analysis since the primary endpoint constitutes safety and tolerability.

PAREXEL International Statistical Analysis Plan

Medivir
Protocol: MIV-711-202

Final 1.0
16 January 2018

The study consists of a Screening period of approximately 2 weeks (Visit 1), eligibility at Visit 2, an open-label treatment period of 26 weeks from Visit 2 through Visit 5, and a follow-up period of 4 weeks (Visit 6) after the last dose of study treatment is administered. Telephone calls will be made 5-9 days after all dosing visits for safety and tolerability. There will be additional phone calls at Week 10 and Week 20 for safety and tolerability.

[figure not shown]
A Data Monitoring Committee (DMC) will meet to review the safety and tolerability data after the first 25 patients complete Visit 4 and Visit 5.

The study design is summarized in the figure below.

PAREXEL International Statistical Analysis Plan

Medivir
Protocol: MIV-711-202

Final 1.0
16 January 2018

*) Patients eligible for the MIV-711-202 study will not do the follow up visit in the MIV-711-201 study but the corresponding visit in the MIV-711-202 study.

PAREXEL International Statistical Analysis Plan

Medivir
Protocol: MIV-711-202

Final 1.0
16 January 2018

3.1 Study Population

The study population will consist of patients with symptomatic and radiographic knee joint OA who have participated in Study MIV-711-201. Patients must be able to provide written consent and meet all the inclusion criteria and none of the exclusion criteria.

3.2 Recruitment, Planned Sample Size and Number of Study Centres

The roll-over of individual patients to Study MIV-711-202 is based on the criteria for study Groups A and B detailed above and is executed by a central person independent from the study with access to the randomisation list and eCRF for Study MIV-711-201. Based on a selection criteria for study Group A and B described earlier in this section, it is anticipated that 50-80 patients will be eligible for participation. Recruitment may be terminated if considered appropriate or necessary by the sponsor.

3.3 Patient Withdrawal and Replacement

In order to perform the intent to treat (ITT) analysis, and to enable safety analyses, all patients who discontinue their randomised medication will be asked to still complete their follow-up visit (visit 6) as outlined in the study schedule. An MRI scan should be completed if withdrawal is after Visit 4. This MRI is only done as a safety parameter and is not to be included in any endpoint analysis.

Patients who withdraw from the study will not be replaced.

Other reasons a patient maybe removed from the study are outlined in Section 5.3 in the protocol.

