### 5.3 Patient Withdrawal and Replacement

In accordance with the Declaration of Helsinki, GCP, and International Conference on Harmonisation (ICH) Guidelines and applicable regulations governing human subject protections, individual patients have the right to withdraw consent at any time without prejudice. At the time of withdrawal of consent, a full efficacy and safety evaluation will be performed if the patient consents.

Patients who withdraw will be asked about the reason(s) for withdrawal, and the presence of any AEs and will be asked to return for a follow-up visit (similar to Visit 6) within 4 weeks following the withdrawal. An MRI scan should be completed if withdrawal is after Visit 4.

If a patient is being withdrawn due to a suspected infection, no biological samples from this patient are allowed to be sent to the laboratory. Samples will be managed according to standard routines at the study site.

In case of discontinuation, the clinical research associate (CRA) should be informed as soon as possible.

If the patient has not yet received any IMP in the current protocol and discontinues from the study, the patient should not participate in any further study related procedure.

Patients who withdraw will return to routine care.

Patients must also be removed from the study by the Sponsor or Investigator for any of the reasons listed below:

- The occurrence of pregnancy in a patient.
- Use of a non-permitted concomitant drug, as defined in Section 6.6.4 where the predefined consequence is withdrawal from the IMP.
- Taking another investigational medicinal agent during patients involvement in the study i.e., from qualification to end of treatment (EOT).
- Any violation of, or deviation from study protocol procedures which, in the judgment of the responsible physician, could adversely affect the patients or the integrity of the study including missing more than 7 consecutive doses or other evidence of significant non-compliance (excluding drug holidays or interruptions that were medically warranted).
- Any clinical AE, laboratory abnormality, inter-current illness or significant worsening of inter-current illness which, in the opinion of the investigator, indicates that continued participation in the study is not in the best interest of the patient.
- Patients who undergo target knee joint replacement during the treatment period will be withdrawn from the study and classified as treatment failures.

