- Serum transaminases (alanine aminotransferase [ALT] and/or aspartate aminotransferase [AST]) > 3 x upper limit of normal (ULN) AND total bilirubin > 2 x ULN (confirmed by subsequent repeat).
- ALT or AST > 3 x ULN (confirmed by repeat visit) with the appearance or worsening of symptoms felt by the Investigator to be potentially related to hepatic inflammation, such as fatigue, nausea, vomiting, right upper quadrant pain or tenderness, fever, rash, or eosinophilia.
- QTcF > 500 ms or increase > 60 ms from time matched baseline (confirmed by repeat

ECG).

- Occurrence of an exclusion criterion which is clinically relevant and affects the patient's safety, if discontinuation is considered necessary by the Principal Investigator and/or Sponsor.

In order to perform the modified intention to treat (mITT) analysis, and to enable safety analyses, all patients who discontinue their medication will be asked to still complete their follow-up visit (Visit 6) as outlined in the study schedule.

Patients who withdraw from the study will not be replaced.

In all cases, the reason(s) for withdrawal must be recorded on the electronic CRF (eCRF).

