## 8.2 Early Termination Visit

All patients who discontinue the IMP because of an AE, or for any other reason, will be asked to complete the safety follow-up visit (Visit 6) as outlined in the study schedule (Table 2). In addition to the assessments described in Section 8.1.6, the following should also be completed:

- Drug accountability
- Return of eDiary
- Physical examination
- Performing knee MRI ( $\pm 5$  days) (if withdrawal is after Visit 4)
- Obtaining optional blood samples for pharmacogenomics, proteomics, genomics, metabolomics and lipidomics and urine samples for proteomics and metabolomics.

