All pre- and post-dose assessments including unscheduled assessments will be included in the data listings. For unscheduled assessments collected pre-dose, the last assessment taken for a time point will be used in the data summaries (summary tables, figures, and statistical analysis); for all post-dose time points, the original assessment for any given time point will be used in the data summaries (summary tables, figures, and statistical analysis).

Descriptive statistics for observed values and derived change from baseline values will be tabulated by visit and study group. Continuous variables will be summarized by study group and visit, as appropriate, using descriptive statistics including: number of observations (n), mean (arithmetic), median, standard deviation (SD), minimum, and maximum. Frequencies and percentages will be used for summarizing discrete (categorical) data by study group and visit, as appropriate. The denominator used when calculating percentages will be the number of patients assessed at a particular combination of study group and study visit, as appropriate.

Safety and efficacy data that are reported as missing will be excluded from all descriptive and non-descriptive data analysis. There will be no imputation of any data. Observations that might be considered spurious (extreme relative to the majority of the data) will not be altered or removed from any presentation of the data, including the calculation of summary statistics (means, medians, etc.), unless approved by the sponsor.

For data listings, all raw data will be reported/displayed exactly as provided. For summaries of quantitative safety data, the minimum and maximum value will be reported exactly as the raw data are reported; measures of central tendency (means, medians) will be reported to one more decimal place than the raw data; measures of variance (SD) will be reported to two more decimal places than the raw data.

Unless stated otherwise there will be no adjustment for multiple comparisons.

PAREXEL International Statistical Analysis Plan

Medivir
Protocol: MIV-711-202

Final 1.0
16 January 2018

In all data presentations ‘Treatment’ will be defined as 200 mg MIV-711. Listings will include all patients and will be sorted by patient number and time point (where applicable). All derived data used in a data summary or statistical analysis will be listed.

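### Early stoppers have no scheduled questionnaires and a barred MRI, so the observed Visit 5 efficacy summaries labelled ITT describe only patients who reach Visit 5

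*SAP*

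**What the plan says.** Protocol 5.3 describes follow-up after stopping in two ways. On withdrawal of consent: "At the time of withdrawal of consent, a full efficacy and safety evaluation will be performed if the patient consents". On stopping medication: "In order to perform the modified intention to treat (mITT) analysis, and to enable safety analyses, all patients who discontinue their medication" are asked to attend Visit 6.

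Protocol 8.2 sets out the visit itself, which is Visit 6: "All patients who discontinue the IMP because of an AE, or for any other reason, will be asked to complete the safety follow-up visit". It continues: "In addition to the assessments described in Section 8.1.6, the following should also be completed". The added items are drug accountability, e-diary return, physical examination, knee MRI ("if withdrawal is after Visit 4") and optional samples. Neither this list nor Visit 6 (Section 8.1.6) includes NRS, WOMAC, ICOAP, global improvement or EQ-5D-5L. Table 2 schedules these at Visits 4 and 5 only, and EQ-5D-5L at Visit 5 only.

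SAP 3.3 repeats that discontinuers are followed so that the ITT analysis can be done, then says of the early-termination scan: "This MRI is only done as a safety parameter and is not to be included in any endpoint analysis".

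SAP 4.6.1 defines ITT as every enrolled patient with at least one dose, and SAP 8 makes ITT the default for efficacy. On missing data, SAP 6 says: "There will be no imputation of any data". Protocol 9.2.2 says LOCF will be used for efficacy.

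**The concern.** The documents give an intention-to-treat analysis as the reason for following patients who stop, but the visit they attend collects no symptom data and its scan may not be used. With nothing imputed, a patient who stops adds nothing to any observed Visit 5 efficacy summary, yet those summaries carry the ITT label.

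If patients who stop do worse than those who stay, Week 52 pain, function and structure will look better than they were in the treated group. The study has no control arm against which such a shift would show. A patient who stops before Visit 4 (Week 14) has no questionnaire at all from the extension study. Patients who withdraw consent and patients who stop for other reasons are also promised different assessments.

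**Working it through.** There is no plan figure to reproduce: protocol 9.2.1 states that the study is unpowered, and no dropout rate is assumed. The check is mainly a comparison of texts.

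**1. What is collected, and what the SAP does with it**

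| Measure | Scheduled in 202 | Early-termination visit (8.2 with 8.1.6) | SAP output at Visit 5 |
|---|---|---|---|
| NRS, WOMAC | Visits 4, 5 | No | Observed summary and mixed model |
| ICOAP, global improvement | Visits 4, 5 | No | Listing only |
| EQ-5D-5L | Visit 5 | No | Observed summary |
| OARSI-OMERACT response | Derived at Visit 5 | Cannot be derived | Listing only |
| Quantitative MRI | Visit 5 | Only after Visit 4; barred | Observed summary and mixed model |
| MOAKS | Visit 5 | Only after Visit 4; barred | Shift tables |
| CTX-I, CTX-II | Visits 2, 4, 5, 6 | Yes, through Visit 6 | Observed summary and mixed model; shells end at Visit 5 |

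As scheduled, no observed Visit 5 MRI or questionnaire result can contain a patient who stopped early. Any questionnaire obtained under 5.3 at consent withdrawal has no stated place in the SAP.

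**2. How many patients**

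Patients without a Visit 5 value = N × d, with N = 50 to 80 (protocol 5.4). The only withdrawal count in the documents is 7 of 102 in the parent study on 21 June 2016 (protocol 2.2): 7/102 = 6.9%.

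- 50 × 0.069 = 3.4; 80 × 0.069 = 5.5.
- Assumed range of 5-20%: 2.5 to 10 of 50, and 4 to 16 of 80.

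The 6.9% is only a marker. The first patient was randomised in March 2016, so no one had more than about 16 weeks of follow-up (1 March to 21 June is 112 days). Extension patients, in turn, have already completed 26 weeks in the parent study.

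**3. Size of the bias**

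Bias in an observed mean = proportion stopping × (completer mean − stopper mean). The documents give neither term for this study, so no figure on the NRS or MRI scale can be derived.

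A simulation shows how the observed mean and the model differ. Assumptions: 65 patients; three visits (201 Visit 2, 201 Visit 8, 202 Visit 5); equal between-visit correlation of 0.5, 0.8 or 0.95; stopping more likely with a worse Visit 8 value; stopping rate of about 6.9%, 15% or 20%; 3,000 runs per setting.

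- Observed Visit 5 mean: too favourable by 0.036 SD (correlation 0.5, 6.9%) to 0.156 SD (correlation 0.95, 20%).
- Likelihood-based mean of the kind in SAP 8.1.1: off by at most 0.004 SD.

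The model does well because the simulation made stopping depend only on a value the model sees. Stopping because of symptoms or adverse events that arise on drug after Visit 8 need not behave that way.

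**4. Group B scans**

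Group B took placebo in 201, and its MRI baseline is 201 Visit 8 (SAP 8). The only scheduled 202 scan is at Visit 5. For a Group B stopper the usable scans are therefore 201 Visits 2 and 8, both before any MIV-711. The barred scan is the only one that follows exposure. LOCF would not help: carrying Visit 8 forward gives a change from baseline of exactly zero.

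**The case against.** **The ITT results are not completers-only.** This is the strongest objection, and it stands. A reader might infer from the gap that all ITT efficacy results describe completers. They do not. The repeated-measures model in SAP 8.1.1, reused for NRS, WOMAC, e-diary NRS and the CTX biomarkers, keeps each stopper's earlier visits, including Visit 4 questionnaires where reached. What remains is that its missing-at-random assumption is neither stated nor tested. The per-protocol MRI analysis is no test, because SAP 4.6.2 removes discontinuers and the ITT stoppers have no Visit 5 scan.

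**The scan is not lost altogether.** SAP 9 plans no MRI safety output, so a reader might infer that nothing is ever done with it. But SAP 6 puts all post-dose assessments, unscheduled ones included, into listings, and imaging listings by visit are planned. It would probably be listed.

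**Barring the scan can be defended.** Under 5.3 the visit falls within 4 weeks after withdrawal, so the scan may be off drug and at a variable time. The protocol itself doubts that cartilage change shows within 6 months (Section 2.3). This is a good reason to keep the scan out of the main model, but not out of a sensitivity analysis.

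**Questionnaires are not uniformly omitted.** Section 5.3 promises a full evaluation at consent withdrawal. So this is a conflict between 5.3 and 8.2 with Table 2, not a settled rule.

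**Knee replacement.** Patients with target-knee replacement "will be withdrawn from the study and classified as treatment failures" under protocol 5.3, and the SAP has no counterpart. A reader might infer a distorted responder rate. SAP 8.3.4 plans only a listing, so a change would alter no table.

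**No evidence of direction.** None of the seven parent-study withdrawals is recorded as knee pain or knee surgery. They do not show that stoppers have worse knees.

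**Conclusion.** The point holds in limited form. The early-termination schedule does not deliver what protocol 5.3 promises or what the stated mITT purpose needs, and SAP 3.3 sets aside the one structural measurement it does collect. Observed Visit 5 summaries of MRI and questionnaires, MOAKS shift tables, EQ-5D-5L and the OARSI-OMERACT response come only from patients who reach Visit 5. The mixed-model estimates depend on missing at random, most heavily for Group B MRI.

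About 3 of 50 to 5-6 of 80 patients would be affected at the parent study's interim rate. The 0.04-0.16 SD from the simulation illustrates its own assumptions and does not estimate bias in this trial. The direction of any bias is likewise an assumption.

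The weight is moderate: the primary endpoint is safety, which discontinuers are followed for; efficacy is secondary or exploratory; and nothing is powered.

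**What to change.** 1. **Schedule.** Add NRS, WOMAC and EQ-5D-5L to protocol 8.2 and Table 2 for every reason for stopping, with ICOAP and global improvement for consistency with 5.3. The cost is a few minutes at a visit already held. Planned conduct ended in August 2017 and the SAP is dated January 2018; if fieldwork is closed, analyse whatever was collected under 5.3 and carry the change into later protocols.

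2. **Scan.** Replace the bar in SAP 3.3 with: *the early-termination MRI is listed with days since last dose and used in one ITT sensitivity run of the 8.1.1 model, entered in the Visit 5 slot as the last on-study scan; the model using scheduled Visit 5 scans only remains the main analysis.* Using the Visit 5 slot leaves visit as a class factor, so the code does not change. SAP 7.9 says the last-dose date is not in the database for withdrawn patients. It must be recovered from source, or days since withdrawal (Listing 16.2.1.1) shown instead. The cost is one model run on scans already acquired, plus central reading if they have not been read.

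3. **Missing data.** Reconcile LOCF (protocol 9.2.2) with no imputation (SAP 6), and record the choice as a change to the planned analysis. State the missing-at-random assumption in SAP 8.1.1, report n at each visit, and label observed Visit 5 summaries as completer data. This costs only text and table footnotes.

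The downside is that some scans and scores will be off schedule and possibly off drug, which is why they belong in a sensitivity analysis only.
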